Methods: This will be a three-arm, cluster randomized trial with crossover conducted in six regions of Ontario, Canada (Peel, Halton, Toronto, Simcoe, London and Ottawa) over a three year period of time. According to randomized cluster assignment, all adult (≥ 18 years) patients presenting in refractory VF (defined as patients presenting in VF/pVT and remaining in VF/pVT after three consecutive standard defibrillation attempts each separated by 2 minutes of CPR) during out-of-hospital cardiac arrest of presumed cardiac etiology will be treated by one of three strategies: (1) continued resuscitation using standard defibrillation; (2) resuscitation involving DSED; or (3) resuscitation involving VC (change of defibrillation pads from anterior-lateral to an anterior-posterior pad position) defibrillation. The primary outcome will be survival to hospital discharge. Secondary outcomes will include neurologic outcome at hospital discharge, return of spontaneous circulation (ROSC), termination of VF after the first interventional shock, termination of VF inclusive of all interventional shocks, and number of defibrillation attempts to obtain ROSC. Based on our previous cohort study research and the DOSE VF pilot RCT, we will also perform an a priori subgroup analysis comparing rates of survival to hospital discharge for those randomized to DSED who receive DSED after three failed successive standard shocks (early DSED or first DSED shock is shock 4-6) to those who receive DSED after six failed successive standard shocks (late DSED or first DSED shock is shock 7 or later).

Impact: A well-designed randomized controlled trial employing a standardized approach to alternative defibrillation strategies early in the treatment of refractory VF is urgently required to determine if the treatments of VC defibrillation or DSED impact clinical outcomes.

Background:

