fibrillation.⁵⁻¹⁰ Recently, case series and individual case reports have surfaced demonstrating conflicting outcomes for patients treated with DSED for refractory VF, both in and outside the hospital.¹¹⁻¹⁶ Cabanas *et al.*, were able to demonstrate improved termination of VF employing a prehospital protocol with use of DSED but reported no improvement in survival. This was likely due to late application of DSED (mean time to first DSED shock was 36.8 minutes, mean number of shocks prior to DSED was eight).¹¹ Ross *et al.*, in a retrospective analysis of 50 DSED cases over a three year time frame, demonstrated no improvement in the primary outcome of neurologically intact survival employing DSED, but did not report data regarding the timing of the DSED shock nor CPR quality.¹² Lybeck *et al.*, and Johnson *et al.*, both described cases of early use of DSED with successful outcomes of neurologically intact survival to hospital discharge.^{13,14} Despite growing enthusiasm, particularly in the field of prehospital medicine, there is a paucity of evidence to support widespread implementation of this therapy. Further, most uses of DSED have been employed as an ad-hoc final effort to convert VF, as opposed to a planned early application of this alternative treatment strategy. From a mechanistic viewpoint, it is unclear whether the change of vector, timing of the “dual shocks” or the application of increased energy is the curative factor for those responding to DSED. Our research group evaluated 251 cases of refractory VF (201 standard care, 50 DSED) over a three-year period beginning on Jan 1, 2015 in four Canadian EMS agencies currently participating in the DOSE VF pilot RCT. Our research demonstrated improved rates of VF termination and ROSC when comparing early DSED (shocks 4-8) to similar shocks provided by standard defibrillation. Specifically, when early defibrillation attempts were considered (defibrillation attempt 4-8), VF termination was higher for those receiving DSED compared to standard defibrillation (29.4% vs. 17.5%; RR: 1.7; 95% CI: 1.1 to 2.6). Additionally, when early defibrillation attempts were

considered (defibrillation attempt 4-8), ROSC was higher for those receiving DSED compared to standard defibrillation (15.7% vs. 5.4%; RR: 2.9; 95% CI: 1.4 to 5.9).

The DOSE-VF Pilot RCT

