Research Question: Among adult (≥ 18 years) patients presenting in refractory VF or pulseless ventricular tachycardia (pVT) during out-of-hospital cardiac arrest, does DSED or VC defibrillation (anterior-posterior compared to anterior-lateral pad position) result in greater rates of survival to hospital discharge compared to standard defibrillation?

Population: Adult (≥ 18 years) patients presenting in refractory VF/pVT during out-of-hospital cardiac arrest. Refractory VF will be defined as patients in whom VF/pVT is the presenting rhythm and whom remain in VF/pVT after three successive failed defibrillation attempts each separated by 2 minutes of CPR.

Intervention: (1) Resuscitation involving DSED, or (2) Resuscitation involving VC defibrillation (anterior-lateral compared to anterior-posterior pad position).

Comparison: Resuscitation using standard defibrillation (pads in anterior-lateral position throughout the resuscitation).

Outcomes: The primary outcome will be survival to hospital discharge. Secondary outcomes will include neurologic outcome at hospital discharge, ROSC, termination of VF after the first interventional shock, termination of VF inclusive of all interventional shocks, and number of defibrillation attempts to obtain ROSC. We will also perform an a priori subgroup analysis comparing rates of survival to hospital discharge for those randomized to DSED who receive DSED after three failed successive standard shocks (early DSED or first DSED shock is shock 4-6) to those who receive DSED after six failed successive standard shocks (late DSED or first DSED shock is shock 7 or later). We will also perform a sensitivity analysis examining the effect of time period (pilot study, pre-COVID, during COVID) on our outcomes.

Inclusion Criteria: ≥ 18 years of age, non-traumatic cardiac arrest of presumed cardiac etiology, with a presenting rhythm of ventricular fibrillation/pVT; with no ROSC or non VF rhythm after three consecutive shocks.

Exclusion Criteria: Traumatic cardiac arrest, patients with pre-existing do not resuscitate orders, , patients in recurrent ventricular fibrillation (defined as those with a secondary presentation of VF (not the presenting rhythm) or those presenting in VF but did not receive three consecutive failed defibrillation attempts). Patient's whose initial care was provided by non-participating EMS agencies or fire services will be excluded.

Methods:

Study Design and Population

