All paramedics treating patients during out-of-hospital cardiac arrest follow a provincial protocol for treatment of patients in VF (**Appendix 1**). Cardiopulmonary resuscitation (CPR) will be performed prior to defibrillator pad application. Each rhythm analysis will occur at standard two-minute intervals. VF will be determined by paramedic manual defibrillator analysis or semi-automatic defibrillator analysis by participating fire services, after which a shock will be provided. For all patients, the first three shocks will occur with defibrillation pads placed in the anterior-lateral position. Epinephrine and antiarrhythmic medication (amiodarone or lidocaine) will be provided as per provincial protocol. For eligible patients remaining in VF after three consecutive shocks (following two-minute CPR intervals) that are delivered by paramedics or participating fire services (defibrillation shocks provided by bystanders prior to EMS arrival will not be counted), all subsequent defibrillations will be randomized to one of the following treatment strategies:

Strategy 1 (**Standard Defibrillation**): For paramedic services randomized to standard defibrillation, all subsequent defibrillation attempts will occur through pads placed in an anterior-lateral configuration as noted in **Appendix 1**.

Strategy 2 (**VC Defibrillation**): For paramedic services randomized to VC defibrillation, all subsequent shocks will be delivered using anterior-posterior pad placement, as noted in Appendix 1. Transfer of pads to the anterior-posterior position from the initial standard anterior-lateral configuration will occur during the two-minute cycle of CPR following the third shock with minimal interruptions in CPR.

Strategy 3 (**DSED**): For paramedic services randomized to DSED, paramedics will apply a second set of defibrillation pads as soon as possible after the first three shocks (via a second

paramedic or fire defibrillator) in the anterior-posterior position, as noted in **Appendix 1**.

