All tests will be 2-sided with $p < 0.05$ denoting statistical significance. The unit of analysis for the comparisons will be the individual patient. All patients will be analyzed according to randomized treatment assignment (intention-to-treat analysis). Based on the DOSE VF pilot RCT secondary analyses will be performed based on actual treatment received, appropriate randomization performed, and appropriate randomization performed with optimal intervention shock timing (shock 4). We will also perform an a priori subgroup analysis comparing rates of survival to hospital discharge for those randomized to DSED who receive DSED after three failed successive standard shocks (early DSED or first DSED shock is shock 4-6) to those who receive DSED after six failed successive standard shocks (late DSED or first DSED shock is shock 7 or later). Last, we will perform a sensitivity analysis to examine the impact of trial phase (pilot study, pre-COVID, and during COVID) on our outcomes. The binary primary outcome, survival to hospital discharge, will be compared across the arms of DSED and VC defibrillation as an adjusted odds ratio with 95% confidence intervals (CIs) using the standard arm as the reference group.²⁷ We will use a generalized linear mixed model (GLMM; logit link) with random effects for cluster-period effect, and using fixed-effects for cluster and for the period, to account for the effect of period on the outcome, as has been recommended for the analysis of cluster crossover trials.^{28,29} The primary analysis will also adjust for the following baseline variables known to impact outcomes after out-of-hospital cardiac arrest: age, sex,

bystander witnessed arrest, bystander CPR provided, time to first arrival, public versus private location, epinephrine and antiarrhythmic use.³⁰ We will also test for effect modification by trial phase, comparing effectiveness in the internal pilot trial and the larger definitive trial. Odds ratios with 95% CIs for secondary outcomes will be calculated in a similar manner, where appropriate.

Consent Waiver

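### The early-versus-late DSED comparison groups patients by an event that happens after assignment, so a survival difference between the groups would not isolate the effect of timing

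*Combined protocol and SAP*

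**What the plan says.** The comparison appears in the abstract's Methods ("Based on our previous cohort study research and the DOSE VF pilot RCT, we will also perform an a priori subgroup analysis"), under Outcomes, and in Statistical Analysis and Mock Tables. It contrasts survival to discharge in "those randomized to DSED who receive DSED after three failed successive standard shocks (early DSED or first DSED shock is shock 4-6") with survival in the other DSED-arm patients ("late DSED or first DSED shock is shock 7 or later").

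The Randomization Strategy section fixes each service's treatment sequence before the study starts. A patient becomes eligible later, after the third failed shock: "For eligible patients remaining in VF after three consecutive shocks". Under Study Protocol, a DSED-arm patient for whom no second defibrillator is available gets standard shocks until one can be found.

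The covariates listed for the primary model do not include shock number. No model, same-shock comparator or landmark is stated for the early-versus-late contrast. The same section adds that "secondary analyses will be performed based on actual treatment received", with two further sets, one of them "appropriate randomization performed with optimal intervention shock timing (shock 4").

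**The concern.** The shock number of a patient's first DSED shock depends on when a second defibrillator arrives, on how many shocks the fire service gave beforehand, and on how long the patient went on needing shocks. The last of these is tied to outcome. Membership of the late group requires at least seven shocks, and membership of the early group requires only four.

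The Sample Size section cites a study in which 30-day survival was 12.4% at 4-10 shocks and 4.9% above 10, and bases the 12% baseline on it. With such a gradient, the late group can do worse because of who can enter it.

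This is the only subgroup comparison that the analysis section calls a priori. It bears on what the DSMB letter treats as central to the protocol, an intervention shock soon after three failures. A result favouring early DSED could easily be read as evidence that timing matters.

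**Working it through.** The plan gives no expected difference, power or sample size for this comparison, so it has no figure to reproduce. The check asks what the contrast would show if DSED and its timing had no effect.

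**Inputs from the documents**
- Survival S: 12.4% at 4-10 shocks, 4.9% above 10 (Sample Size). This is 30-day survival, standing in for survival to discharge.
- VF termination at standard shocks 4-8: 17.5% (Background).
- 90.2% of pilot patients had an intervention shock before shock 6 (pilot section; not DSED-specific).
- 122 DSED-arm and 128 standard-arm patients (DSMB letter, January 2022; one service was to continue).

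**Assumptions**
- After each shock from the fourth on, the shock sequence ends with probability p = 0.10, 0.175 or 0.30.
- From shock 4 on, a second defibrillator becomes available with probability a per shock, independent of prognosis. Values run from a = 0.4 up to 0.72-0.78. The upper values solve a + (1−a)(1−p)a = 0.902.

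**Direction.** A patient can first receive DSED at shock k only if the total shock count K is at least k. Under no effect, expected survival is E[S(K) | K ≥ k]. If S never rises with K and delay is unrelated to prognosis, this cannot rise with k, whatever the distribution of K.

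**Size, using the cited bands (a step after shock 10).** For k ≤ 10, P(K > 10 | K ≥ k) = (1−p)^(11−k), so survival in % is 12.4 − 7.5(1−p)^(11−k). For k ≥ 11 it is 4.9. The share of the arm first given DSED at shock k is a·r^(k−4), with r = (1−p)(1−a).

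Example with p = 0.175 and a = 0.4, so r = 0.825 × 0.6 = 0.495:
- Survival at first DSED shock 4, 5, 6: 10.45, 10.04, 9.53. Weights 1, 0.495, 0.245. Early = (10.45 + 4.97 + 2.34)/1.740 = 10.2%.
- Survival at shock 7, 8, 9, 10, 11 or later: 8.93, 8.19, 7.30, 6.21, 4.9. Relative weights 1, 0.495, 0.245, 0.121, 0.119. Late = 16.11/1.980 = 8.1%.
- Gap about 2.1 points; OR = (10.20/89.80)/(8.13/91.87) = 1.28.
- Late group: 122 × 0.4 × 0.495³/0.505 = 11.7. Early group: 122 × 0.4 × (1 − 0.495³)/0.505 = 84.9. Never given DSED: 122 − 96.6 = 25.4.

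**Ranges over all values of p and a, with K uncapped or capped at 15**

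| Survival by shock count | Null early:late OR | Gap, points |
|---|---|---|
| Flat, 12% | 1.00 | 0 |
| Step, cited bands | 1.14-1.28 | 1.3-2.1 |
| Smooth exponential decline fitted to both bands (assumed) | 1.32-1.57 | 1.9-3.7 |

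The expected late group is about 6-17 of 122 at a = 0.4 and about 0-2 at pilot-like availability.

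A different set of assumptions (p from 5.4% to 35%, fixed mixes of early starts, all late starts at shock 7) gives 1.08-1.20 with the bands and 1.39-1.70 with a smooth curve. The size therefore depends on the model.

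**If delay is related to prognosis.** Take two equal groups in which the better-prognosis half waits longer, again under the step model:
- survival ×1.2 with a = 0.4 and ×0.8 with a = 0.6: OR 1.05-1.12
- ×1.2 with a = 0.6 and ×0.8 with a = 0.78: OR 0.99-1.06
- ×1.3 with a = 0.6 and ×0.7 with a = 0.78: OR 0.92-0.98

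The smooth model stays at 1.07 or more in all three.

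**Chance findings.** With 122 patients and a = 0.4, simulated null trials put early DSED numerically ahead in 61-71% of cases, against 52-55% with no gradient. Fisher p < 0.05 favouring early DSED occurs in under 2% in every scenario.

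**The case against.** The strongest objection is that a survival gradient alone does not fix the direction. The DSMB letter describes fire crews giving several shocks before paramedics arrive. Such patients may have had an earlier first shock and yet a later first DSED shock, so delay could go with better prognosis. The illustrative mixes above show that this can remove or reverse the step-model bias. This stands, and the claim on direction is conditional on it.

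Second, the documents give a single 12.4% band for 4-10 shocks. It covers every early start and many late patients, so a difference between 4-6 and 7-10 shocks is not documented. This also stands. The step figures therefore lead, and the smooth curve is only an assumption.

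Third, the consequence is limited: one subgroup analysis, possibly with a handful of late patients, which the plan nowhere calls proof of a timing effect. This is true and limits the severity. It does not make the contrast interpretable.

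A reader might also infer more than the documents support:
- **That the trial's main result is biased.** The primary analysis is by randomised assignment and does not use this grouping.
- **That false-positive findings would be inflated.** The simulated rate above does not show this.
- **That the shock-4 set shares the fault.** An eligible patient is still in VF after shock 3, so selecting on an intervention at shock 4 does not select on later shocks. Under the same null its odds ratio against the standard arm is 1.00. Its remaining risk is confounding by availability or compliance.

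The analysis by treatment actually received does select on events after assignment. If DSED-arm patients never given DSED are counted as standard, its null odds ratio is 0.83-0.99.

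**Conclusion.** The point holds with conditions. Confidence is high that the contrast selects on events after assignment, and that nothing in the readable text corrects for this. Blinded confirmation of the subset, described under Data Collection, guards against misclassification and not against selection.

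Confidence is moderate that the bias favours early DSED. That requires survival to fall with shock count, and delay to be unrelated to prognosis or to go with a worse one.

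Confidence is low on size: a null odds ratio of about 1.14-1.28 with the cited bands, 1.32-1.57 under an assumed smooth decline, and about 0.92-1.12 in mixes where delay goes with better prognosis. It would be too strong to conclude that early DSED must look better. What can be said is that, whichever way the bias runs, the contrast does not isolate timing.

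Appendix 3, with the mock tables, and the text after the heading on approval of the protocol were not available, so a caveat there cannot be ruled out.

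**What to change.** In the abstract, under Outcomes and in the analysis section:

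- State that the direct early-versus-late contrast is exploratory and non-randomised and will not be used as evidence on timing. Report the numbers early, late and never given DSED.
- As the comparative analysis, set DSED-arm patients first given DSED at shock k against standard-arm patients still in VF and receiving shock k. Pool into 4-6 and 7 or later, with shock number as a stratum. The group's own cohort did something close for VF termination and ROSC, "comparing early DSED (shocks 4-8) to similar shocks provided by standard defibrillation".
- Keep the planned cluster and period terms, and use standard errors that allow for standard-arm patients appearing at more than one shock. In simulations without cluster and period terms, ignoring the repetition gave a 7-8% false-positive rate in the 4-6 band, against 3.5-5.1% with patient-clustered errors.
- Set a minimum number of late survivors in advance. Below it, report counts only for the late band.
- Label the analysis by treatment actually received non-randomised too. Keep intention-to-treat primary, as planned.

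**Cost.** A few sentences and modest programming; shock times, shock types and VF termination after each shock are already abstracted.

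**Downside.**
- At 122 versus 128 patients, the standard error of the log odds ratio in the 4-6 band is 0.42-0.53. The 95% limits then lie exp(1.96 × 0.42) = 2.3-fold to exp(1.96 × 0.53) = 2.8-fold either side.
- The late band was estimable in only 36-68% of simulated trials at a = 0.4, and in 10% or fewer at pilot-like availability.
- The same-shock comparison asks whether DSED beats standard shocks at a given point, which answers the timing question only indirectly.
- Confounding remains if second-defibrillator arrival is related to prognosis. In an illustrative null case with survival ×1.2 and ×0.8 and availability 0.6 and 0.4, the same-shock odds ratio was 1.02-1.03 for shocks 4-6 and 0.90 for shocks 7-10. With availability reversed it was 0.97-0.98 and 1.10.

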This will be a three-arm, cluster randomized trial with crossover conducted in six regions of Ontario, Canada (Peel, Halton, Toronto, Simcoe, London and Ottawa). These six regions were

selected because each has its own paramedic service, and all have previously participated in and successfully completed prehospital resuscitation trials.^{19,20} Two treatment strategies (DSED and VC) will be simultaneously assessed against a common control group (standard defibrillation). This approach has been chosen to maximize efficiency, allowing comparison of two new treatments to usual care in a single three-armed randomized trial.^{21,22}

The clusters will be defined by the paramedic service in each of the six regions and each cluster will crossover at least twice per year to receive one of three treatment approaches (standard care, DSED or VC) for six months. Each service will apply each of the three treatment arms twice over the duration of the study. The annual prevalence of paramedic treated out-of-hospital cardiac arrest for these regions is approximately 4,000; of which 800 (20.0%) patients will present in VF. Our pilot trial suggests that approximately 180 patients per year will meet the study criteria for refractory VF. The study protocol will be approved by each local institutional Research Ethics Board and is registered with clinicaltrials.gov. (<https://clinicaltrials.gov/ct2/show/NCT04080986>).

All adult (≥ 18 years) patients remaining in refractory VF or pVT during out-of-hospital cardiac arrest of presumed cardiac etiology will be eligible for inclusion. Patients suffering a traumatic cardiac arrest, patients with pre-existing do not resuscitate orders and patients in recurrent ventricular fibrillation (defined as secondary presentation of VF or those presenting in VF but did not receive three consecutive defibrillation attempts) will be excluded. Patient's whose initial care was provided by non-participating EMS agencies or fire services will be excluded.

Study Protocol:

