In response to the need for more efficient trial designs that accelerate discovery and minimize costs, it has been recommended that researchers consider employing multi-arm trials designed for logistical efficiency.²¹ In a multi-arm trial, several treatments are simultaneously assessed against a common control group within a single randomized trial, allowing sizeable gains in efficiency. Relative to conducting separate trials for each experimental treatment, a multi-arm design has been shown to require a lower total sample size and financial resources than separate, sequential two-arm trials.²²

From our internal pilot trial discussed earlier, we observed that across our paramedic services, the annual prevalence of paramedic treated out-of-hospital cardiac arrest for these regions is approximately 4,000; of which 800 (20.0%) patients will present in VF. Our pilot data suggests that approximately 180 patients per year meet the study criteria for refractory VF. Holmen et al.²⁴ demonstrated a 30 day survival rate of 28.7% for patients receiving 1-3 shocks, declining to 12.4% for those receiving 4-10 shocks, and 4.9% for those receiving greater than 10 shocks. Based on these findings, we assumed a baseline survival rate of 12% for patients who will meet our study criteria. This baseline survival rate will be confirmed by comparing to the baseline survival rate of the standard defibrillation arm of the pilot RCT and will be adjusted according to this value.

We hypothesize that DSED and VC defibrillation earlier in the resuscitation will result in survival as high (or higher) as standard defibrillation. We project a minimum absolute increase of 8% in survival to hospital discharge when VC or DSED strategies are employed as per our protocol, compared to standard care.

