General Characteristics: Study ID, Emergency health service, Fire service if applicable, age, sex, weight (approximate), arrest location (public/private), response time, bystander CPR, bystander AED, bystander shock, bystander witnessed, highest service level on scene (ALS vs BLS).

General Date/Time Information: Date of Call, call arrival to 911, arrival at scene (wheels stop 1st vehicle), arrival at patient side, time of first rhythm, second, etc. (all shocks), first shock, second shock, etc.(all shocks), depart scene, arrival at hospital.

Prehospital Treatment Data: Arrest occurred after EMS arrival (witnessed EMS), AED/Defib applied, total shocks delivered, number of each shocks (standard, vector change, DSED), time of first ROSC post arrest (ROSC will be defined as the restoration of a spontaneous rhythm noted on the defibrillator files with a corresponding palpable pulse noted on the paramedic ambulance call report) and termination of VF (defined as the absence of a shockable rhythm 2 minutes after each interventional or standard shock).

CPR quality characteristics: Median CCF during resuscitation, median compression rate during resuscitation, median compression depth during resuscitation.

Specific shock variables (for each shock): Pre-shock pause, post-shock pause, number of interventional or standard shocks that resulted in ROSC, rate of re-arrest post-ROSC.

Variables to be abstracted from a combination of electronic defibrillator files and the ACR

The data abstractor will use a combination of both electronic defibrillator files and the ACR to determine VF termination, time of first ROSC, as well as the number of defibrillatory shocks provided to first ROSC. All defibrillator files will be reviewed by two independent investigators blinded to the intervention to confirm VF termination as well as the subset of cases that meet the criteria for our subgroup analysis. Adjudication by a third investigator blinded to the intervention will occur should consensus be required.

Data linkage to administrative data bases at Cancer Care Ontario CCO:

The primary outcome of survival to hospital discharge will be obtained through linkage of our data with the administrative databases at Cancer Care Ontario (CCO). In addition we plan on collecting data regarding whether or not a patient had coronary angiography and/or

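### The primary model's only witness covariate is bystander-witnessed arrest, so EMS-witnessed arrests, which are eligible and recorded separately, have no category of their own

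*Combined protocol and SAP*

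**What the plan says.** The Statistical Analysis section specifies the primary model: "We will use a generalized linear mixed model (GLMM; logit link) with random effects for cluster-period effect", with fixed effects for cluster and period. It continues: "The primary analysis will also adjust for the following baseline variables known to impact outcomes after out-of-hospital cardiac arrest". The list has eight items: age, sex, the run "bystander witnessed arrest, bystander CPR provided, time to first arrival", public or private location, epinephrine use and antiarrhythmic use. Bystander-witnessed arrest is the only witness-status term. No levels or reference category are given for it.

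The abstraction list under Data Collection has two separate fields. General Characteristics contains "bystander shock, bystander witnessed, highest service level on scene (ALS vs BLS". Prehospital Treatment Data contains "Arrest occurred after EMS arrival (witnessed EMS". Response time, the time of the 911 call, arrival at scene and arrival at the patient's side are also abstracted. No time of collapse is listed.

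Study Design and Population excludes "Patients suffering a traumatic cardiac arrest, patients with pre-existing do not resuscitate orders and patients in recurrent ventricular fibrillation", and then patients first treated by non-participating agencies. Arrests witnessed by EMS are not excluded there or under Exclusion Criteria.

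**The concern.** The covariates are chosen because they predict outcome. An arrest in front of the crew and an unwitnessed arrest with no bystander help are opposite cases: the first is attended from collapse, and the second has an unknown time without treatment. On a plain reading of the list, both have the same two values (not bystander-witnessed, no bystander CPR). The third related covariate does not separate them either. For most patients, time to first arrival stands in for time in arrest. For an EMS-witnessed patient the call was made before the arrest, so a long interval does not mean a long delay to treatment.

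Two things are at stake. The adjustment recovers less precision than the recorded data allow. If one arm happens to receive more EMS-witnessed patients, the primary model cannot correct for it. A smaller practical point is that no rule is given for covariates that do not apply. If the bystander fields were left blank for EMS-witnessed arrests, a complete-case fit would drop those patients from an analysis intended to include everyone randomised.

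**Working it through.** No figure in the plan depends on this point, so there is none to reproduce. The check is textual, followed by an illustration of size.

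**1. How the listed covariates treat three kinds of patient (plain reading)**

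| Patient | Bystander witnessed | Bystander CPR | Call-to-arrival interval |
|---|---|---|---|
| Bystander-witnessed | yes | yes or no | time from call, close to time in arrest |
| Unwitnessed, unassisted | no | no | lower bound on time in arrest |
| EMS-witnessed | no | no | recorded, but precedes the arrest |

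The last two rows agree on both bystander terms. The field that separates them is collected but is not in the model.

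**2. How much information the yes/no term would keep**

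All inputs here are assumptions: unwitnessed arrests are 30% of patients with 8% survival, bystander-witnessed arrests have 15% survival, and EMS-witnessed arrests are a share f with survival s. Survival in the merged 'not bystander-witnessed' group is (0.30 × 0.08 + f × s) / (0.30 + f).

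| s | f = 5% | f = 10% | f = 15% |
|---|---|---|---|
| 15% | 9.0% | 9.8% | 10.3% |
| 20% | 9.7% | 11.0% | 12.0% |
| 30% | 11.1% | 13.5% | 15.3% |

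For example, s = 20% and f = 10% gives (0.024 + 0.020) / 0.40 = 11.0%. At s = 15–20% the merged group stays at 9–12%, below the assumed 15%, so the term still predicts. It loses nearly all information only at s = 30% with a large share.

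**3. Effect on the treatment estimate when arms are balanced**

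Simulated logistic models, 310 against 310 patients, no clustering, 800 runs per scenario. Assumptions: 60% bystander-witnessed with odds ratio 2 against unwitnessed; EMS-witnessed 5–15% with odds ratio 2–4.

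- Treatment odds ratio: 1.83–1.86 with yes/no coding, 1.84–1.88 with three levels.
- Power: 74–80% with yes/no coding, 76–80% with three levels. The difference is at most about 2 points.

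**4. Effect when arms differ by chance**

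Large-sample limits with a true treatment odds ratio of 1.00, calibrated to the plan's figure ("we assumed a baseline survival rate of 12% for patients who will meet our study criteria") and with 60% bystander-witnessed in each arm:

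| EMS-witnessed share, control vs active | EMS odds ratio 2 | EMS odds ratio 4 | Three levels |
|---|---|---|---|
| 7.5% vs 12.5% | 1.03 | 1.08 | 1.00 |
| 5% vs 15% | 1.06 | 1.16 | 1.00 |

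**5. How likely such imbalance is**

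Assume a 10% share and simple binomial sampling. The standard deviation of the between-arm difference is √(2 × 0.10 × 0.90 / n).

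- Planned 310 per arm: 2.4 points. A gap of 5 points or more in either direction has probability about 4%.
- About 125 per arm (the DSMB letter reports 122, 128 and 129): 3.8 points. A gap of 5 points or more has probability about 19%, and a gap of 10 points or more about 0.8%.

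This ignores clustering.

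**The case against.** The strongest reply is that no mis-coding is shown. The plan names the covariate without levels, both fields are collected, and the mock tables in Appendix 3, which are not in the text available here, might show the categories. That is right about coding: yes/no is the plain reading, not a documented fact. It does not remove the point. The plan has named its witness covariate, the name matches one of two recorded fields, and the other field is not in the model.

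A reader might go further and infer that EMS-witnessed patients will have negative or missing arrival times and so be lost. The documents do not support that. Call and scene-arrival times are abstracted, and an interval from call to arrival exists and is positive for these patients. A negative value would need a collapse-based clock, and no collapse time is collected. What survives is that the interval means something different for them.

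A reader might also infer that the witness term carries no information. That needs about 30% survival in EMS-witnessed patients, which is above the 28.7% that the Sample Size section cites for patients needing only one to three shocks. Everyone enrolled here has already failed three, and the same section cites 12.4% for four to ten shocks.

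Finally, an extra level is not free. With 379 patients, survivors number about 0.12 × 379 ≈ 45 at control survival throughout, or about (0.12 + 0.20 + 0.20)/3 × 379 ≈ 66 if both active arms gain the planned 8 points. A 5–15% share is about 19–57 patients. The model already carries two treatment contrasts, cluster and period effects and eight covariates. This objection stands as a cost.

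**Conclusion.** The point holds as a minor weakness in the primary model's covariates. A recorded baseline factor that distinguishes two very different kinds of patient is left out, and the plain reading merges them.

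It would be tempting to call the model mis-specified or the treatment effect biased. Neither is supported. Assignment is randomised, so coarse coding of one prognostic factor favours neither arm systematically. The shifts to 1.03–1.16 arise only under an imposed imbalance, and the upper end needs both a 10-point gap and a strong prognostic effect. The expected cost is a small loss of precision (at most about 2 points of power) and no protection against chance imbalance. A 5-point imbalance becomes more plausible at the enrolment reported in the DSMB letter than at the planned size.

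Every size quoted rests on assumed shares and survival for EMS-witnessed patients and on calculations without clustering. The documents give neither quantity, so the true size is unknown.

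**What to change.** In the primary model, replace the bystander-witnessed term with a three-level witness status: unwitnessed, bystander-witnessed, EMS-witnessed. State in advance how the two related covariates are set for EMS-witnessed patients. For example, give bystander CPR and time to first arrival a constant value, with the EMS-witnessed level absorbing the difference. State that no patient is dropped because a bystander or arrival field does not apply. If the sponsor already codes witness status this way, one sentence saying so settles that part.

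The cost is one more parameter, possibly sparse, in a model with few survivors. Both fields are already abstracted, so no new data are needed.
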